7.6 Second Malignancy

Second malignancies require routine reporting to Cortice Bioscience.

7.7 Pregnancy

If a patient inadvertently becomes pregnant while on treatment with TPI 287, the patient will immediately be removed from the study. The site will contact the patient at least monthly and document the patient's status until the pregnancy has been completed or terminated. The outcome of the pregnancy will be reported to Cortice Biosciences without delay and within 24 hours if the outcome is a serious adverse event (e.g., death, abortion, congenital anomaly, or other disabling or life threatening complication to the mother or newborn). If a male patient's partner becomes pregnant on study, the pregnancy must be reported to Cortice Biosciences. The study investigator will make every effort to obtain permission to follow the outcome of the pregnancy and report the condition of the fetus or new born to Cortice Biosciences.

8. PHARMACEUTICAL INFORMATION

A list of the adverse events and potential risks associated with TPI 287 administered in this study can be found in Section 7.1.2.

Metabolism

In vitro studies have shown that TPI 287 is rapidly metabolized by pooled human S-9 liver fractions with an elimination half-life (t1/2) of 58.5 minutes. Seven putative phase 1 (modification) metabolites were detected. Structures of the two main metabolites (TPI 511 and TPI 513) were confirmed to be dihydroxyl and epoxy derivatives. Based on this and the well-established metabolism of other taxanes by cytochrome P450 3A4 (CYP3A4) and cytochrome P450 2C8 (CYP2C8), the use of drugs or herbal supplements that are known to be strong inhibitors/inducers of CYP3A4 and CYP2C8 are not permitted (Investigator's Brochure).

Supply/Storage

TPI 287 Injection should be stored in the provided packaging (vial) in the upright position, at room temperature (between 68-77°F; 20-25°C) away from direct sunlight. TPI 287 Injection must be diluted prior to administration. TPI 287 injection, 10 mg/mL that has been diluted in the IV bag of 0.9% Sodium Chloride, should be stored at room temperature. The diluted TPI 287 must be prepared within 12 hours of use.

9. CORRELATIVE STUDIES

9.1 Laboratory Correlative Studies

PK studies are optional. However, efforts will be made to obtain PK analysis from at least one patient per dose level.

Cerebrospinal Fluid (CSF) PK

CSF samples will be collected 2-3 hours after completion of TP 287 infusion on day 8 of treatment given there is no contraindication for lumbar puncture.

Patient will undergo lumbar puncture in department of interventional radiology. Procedure will be performed under fluoroscopy.

PK analysis will be performed at Moffitt Cancer Center.

Serum PK

Blood will be collected at the same time as lumbar puncture (2-3 hours post-infusion of TPI 287) on day 8 of treatment.

The blood samples will be processed to plasma and the concentration of TPI 287 will be determined using a validated liquid chromatography/tandem mass spectrometry (LC/MS-MS) method at Moffitt Cancer Center.

CSF/Plasma TPI concentration ratio will be calculated.

10. STUDY CALENDAR

Baseline evaluations are to be conducted within 1 week prior to start of protocol therapy. MRI scans must be done ≤ 2 weeks prior to the start of therapy. In the event that the patient's condition is deteriorating, laboratory evaluations should be repeated within 48 hours prior to initiation of the next cycle of therapy.

	Baseline Concurrent phase		Single agent phase		Final [†]	Follow up ^g
		D1	D8	D15		
TPI-287 infusion		Х	Х	Х		
XRT ^a		Х				
Informed Consent	X					
History and Con-meds	Х	х	Х	Х	Х	Х
Baseline Symptoms ^b	X					
Performance status (Karnofsky performance status/ECOG)	Х	Х	Х	Х	Х	Х
Physical Examination (including neurological assessment)	Х	Х	Х	Х	Х	Х
Vital signs and Height/Weight	X	Х	Х	Х	Х	Х
Documenting status of systemic disease	X	X	Х	Х	Х	X
Adverse event evaluation		Х	Х	Х	Х	Х
Quality of life assessment (QLQ-BN20 and QLQ-C15-PAL)	X	X	Х	Х	Х	X
Steroid use assessment	Х	Х	X	Х	X	Х
Blood ^c	Х	Х	Х	Х	Х	
B-HCG	Х					
Radiological assessment ^d	Х					Х
PK samples ^e			X			
Mini-Mental State Examination	Х	Х	Х	Х	Х	X
Lumbar puncture			Х			

^a Radiotherapy will be delivered once daily Monday through Friday, D1-5 for a total of 5 treatments.

^b Baseline symptoms include symptoms occurring on D1 prior to receiving TPI 287 and within 1 week prior.

^c Blood will include CBC and differential, sodium, potassium, chloride, creatinine, AST, ALT, bilirubin, ALP, albumin, calcium, magnesium, phosphate.

^d Radiologic assessment, MRI brain with and without gadolinium, will be performed at pre-treatment and every three months following the end of treatment until the patient is off-study or reaches the 18 month study completion date.

^e PK samples (blood and CSF) will be collected on D8.

^fA final visit will be performed approximately 30 days following completion of treatment with FSRT and/or TPI-287 (whichever treatment occurs last).

^g Information pertaining to survival and long term assessment of the subject's disease status and adverse events will be collected approximately every 12 weeks beginning after the final visit for period of up to 18 months.

11. MEASUREMENT OF EFFECT

Although response is not the primary endpoint of this trial, patients with measurable disease will be assessed by standard criteria. For the purposes of this study, patients should be re-evaluated every 3 months. The serial MRI scans shall be examined at the institution by an independent reviewer, a neuroradiologist. The evaluation of scans will be compared to and corrected with the patient's clinical course. In addition to a baseline brain MRI, confirmatory MRIs will also be obtained 4 weeks following initial documentation of an objective response.

11.1 Antitumor Effect

Definitions

Evaluable for toxicity. All patients will be evaluable for toxicity from the time of their first treatment with TPI 287.

Evaluable for objective response. Only those patients who have received at least one dose of TPI 287 concurrent with FSRT, and have had their disease re-evaluated will be considered evaluable for response. These patients will have their response classified according to the definitions stated below.

Methods for Evaluation

All measurements should be taken and recorded in metric notation using a ruler or calipers. All baseline evaluations should be performed as closely as possible to the beginning of treatment and never more than 2 weeks before the beginning of the treatment.

The same method of assessment and the same technique should be used to characterize each identified and reported lesion at baseline and during follow-up.

Evaluation of Target Lesions

Complete Response (CR): The tumor is no longer seen on two sequential MRI scans, and the patient is on no steroids or only adrenal-maintenance dose of steroids.

Partial Response (PR): \geq 50% decrease in the product of two diameters of target lesions on two sequential MRIs, taking as reference the baseline product of two diameters, provided that the patient has not had his/her dose of steroids increased since the last evaluation period.

Minor Response (MR): Decrease in diameter products of < 50% on two sequential MRI scans provided that the patient has not had his/her dose of steroids increased since the last evaluation.

Stable Disease (SD): The scan shows no change, taking as reference the smallest product of diameters while on study. Patient should be receiving stable or decreasing doses of steroids.

Progressive Disease (PD): > 25% increase in the product of two diameters of target lesions; taking as reference the smallest product on study (this includes the baseline product if that is the smallest on study), provided that the patient has not had his/her dose of steroids decreased since the last evaluation period. A concomitant decrease in steroid dose will rule out a progression designation at this point. The appearance of one or more new lesions is also considered progressions.

Furthermore, the response will be also measured with RANO working group criteria for metastatic brain tumors when this guideline is published.

Duration of Response

Duration of overall response: The duration of overall response is measured from the time measurement criteria are met for CR or PR (whichever is first recorded) until the first date that recurrent or progressive disease is objectively documented (taking as reference for progressive disease the smallest measurements recorded since the treatment started).

The duration of overall CR is measured from the time measurement criteria are first met for CR until the first date that progressive disease is objectively documented.

Duration of stable disease: Stable disease is measured from the start of the treatment until the criteria for progression are met, taking as reference the smallest measurements recorded since the treatment started, including the baseline measurements.

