3. PATIENT SELECTION

3.1 Eligibility Criteria

- Patients must have histologically or cytologically confirmed non-central nervous system primary breast or non-small cell lung cancer.
- Patients must have pathologically or radiologically confirmed metastatic disease in the brain.
- Patients with up to 3 brain metastases (symptomatic and non-symptomatic) can be treated on this study. Maximum diameter of each brain lesion should be ≤ 5 cm. Maximum tumor volume ≤ 120 cc
- Age ≥ 18 years.
- ECOG performance status ≤ 2 (Karnofsky $\geq 60\%$, see Appendix A).
- Life expectancy of greater than 12 weeks.
- Patients requiring treatment with corticosteroids are eligible.
- Treatment with non-enzyme inducing anti-seizure medications is allowed.
- Patients must have normal organ and marrow function as defined below:
 - leukocytes ≥3,000/mcL
 - absolute neutrophil count \geq 1,500/mcL
 - platelets $\geq 100,000/mcL$
 - total bilirubin within normal institutional limits
 - AS T(SGOT)/ALT (SGPT) ≤2.5 × institutional upper limit of normal
 - creatinine within normal institutional limits OR
 - calculated creatinine clearance $\geq 60 \text{ mL/min}/1.73 \text{ m}^2$ for patients with creatinine levels above institutional normal.
- Systemic chemotherapy washout period ≥ 7 days. For investigational dugs and monoclonal antibodies washout period $\geq 5x$ drug half-life. There are no limitations on

number of prior treatment regimens.

- The effects of TPI 287on the developing human fetus is unknown. For this reason, women of child-bearing potential and men must agree to use adequate contraception (hormonal or barrier method of birth control; abstinence) prior to study entry and for the duration of study participation. Should a woman become pregnant or suspect she is pregnant while she or her partner is participating in this study, she should inform her treating physician immediately. Men treated or enrolled on this protocol must also agree to use adequate contraception prior to the study, for the duration of study participation, and 4 months after completion of TPI 287 administration.
- Prior brain surgery or radiation is allowed as long as the metastatic lesion(s) to be targeted in this study has not previously been treated with radiation.
- Ability to understand and the willingness to sign a written informed consent document.

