5.5 General Concomitant Medication and Supportive Care Guidelines

Because there is a potential for interaction of TPI 287 with other concomitantly administered drugs through the cytochrome P450 system, the use of drugs or herbal supplements that are known to be strong inhibitors/inducers of CYP3A4 and CYP2C8 are not permitted (Appendix B).

Prophylactic use of corticosteroids is allowed during the study to limit symptoms from metastases or radiation.

Non-enzyme inducing anti-epileptic drugs may be utilized to control or prevent seizures.

Principal Investigator should be alerted if the patient is taking any agent known to affect or with the potential to affect selected CYP450 isoenzymes.

5.6 **Duration of Therapy**

Patients will receive TPI 287 on days 1, 8, and 15 (total of 3 doses). On day 1, the TPI 287 will be administered 4 (+/-2) hours prior to FSRT.

5.7 **Duration of Follow Up**

Patients will be seen in follow-up on the 3rd, 6th, 9th, 12th, 15th, and 18th month following the first day of treatment with TPI 287. Patients will be followed for 18 months after first treatment on study or until death, whichever occurs first.

The following will be obtained at pre-treatment evaluation and at each follow up visit: Symptoms history, vital signs/ height and weight, physical examination, KPS/ECOG score, Mini-Mental State Examination, steroid use, quality of life questionnaire, and toxicity evaluation.

Radiologic assessment, MRI brain with and without gadolinium, will be performed at pretreatment and every three months following the end of treatment until the patient is off-study or reaches the 18 month study completion date.

Furthermore, the principal investigator will have close collaboration with oncologists treating the systemic malignancy. Information regarding the status of systemic malignancy such as results of standard imaging evaluations, serum biomarkers measurements, and systemic treatments will be collected and recorded at each visit.

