5.8 Criteria for Removal from Study

Patients will be removed from study when any of the below criteria applies:

- Disease progression requiring therapy not allowed in the protocol, including whole brain radiation.
- Intercurrent illness that prevents further administration of treatment: a condition, injury, or disease unrelated to cancer, that renders TPI 287 or radiation treatment unsafe or regular study visits impossible, including, but not limited to, active infection, symptomatic congestive heart failure, unstable angina pectoris, cardiac arrhythmia, pregnancy, or psychiatric illness that would limit compliance with study requirements.
- Unacceptable adverse event(s) (see adverse events)
- Patient decides to withdraw from the study
- General or specific changes in the patient's condition that render the patient ineligible for the study
- Non-compliance with study treatment or protocol-required evaluations and study visits
- Inability of subject to comply with study requirements
- Determination by the investigator that it is no longer safe for the patient to continue therapy
- Patient who inadvertently becomes pregnant (see reporting of pregnancy)

Patients may withdraw at any time or be dropped from the study at the discretion of investigator should any untoward effects occur. In addition, a patient may be withdrawn by the investigator if he/she violates the study plan or for administrative and/or other safety reasons. The investigator or study coordinator must notify Cortice Biosciences immediately when a patient has been discontinued/withdrawn due to a serious adverse experience. All trial treatment-related toxicities and SAEs at the time of discontinuation/withdrawal should be followed until resolution or stabilization. Patients who are discontinued from the study will still be followed for disease progression.

All deaths that occur within the trial period or within 30 days after administration of the last dose of trial drug must be reported to Cortice Biosciences for the purposes of serious adverse event (SAE) reporting; however, deaths due to progression are not SAEs.

Patients who discontinue from the study for reasons unrelated to the study (e.g., personal

reasons, or adverse events after registration but prior to receiving study therapy) may be replaced as required for the study to meet its objective. The replacement will generally receive the same treatment or treatment sequence (as appropriate) as the allocation number replaced.

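### The response rate leaves out treated patients who have no post-treatment scan, although the first scheduled scan is about three months after treatment

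*Combined protocol and SAP*

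**What the plan says.** Section 11.1 (Antitumor Effect) defines two populations. For toxicity, every patient counts from the first TPI 287 treatment. For objective response, only those who "have received at least one dose of TPI 287 concurrent with FSRT, and have had their disease re-evaluated will be considered evaluable for response" count, and only they receive a response category. The categories are read from MRI. Complete response, for example, requires that "The tumor is no longer seen on two sequential MRI scans", and partial response also needs two consecutive scans. Section 11 adds that "confirmatory MRIs will also be obtained 4 weeks following initial documentation of an objective response".

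On timing, section 5.7 sets clinic visits from the 3rd "month following the first day of treatment with TPI 287" and brain MRI at baseline and then "every three months following the end of treatment until the patient is off-study". Footnote d of the Study Calendar (section 10) repeats the MRI rule. Footnote f says that a "final visit will be performed approximately 30 days following completion of treatment with FSRT" and/or TPI 287, whichever ends last; the calendar marks no imaging at that visit. Section 3.1 requires "Life expectancy of greater than 12 weeks".

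Section 14.2 plans 10 patients at the MTD, including those treated at that dose during escalation, partly to assess radiologic response. Section 14.3 plans counts and percentages. It gives no response denominator and no rule for missing scans.

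**The concern.** Whether a patient is re-evaluated is known only after treatment and depends on how the patient does. With the first scheduled scan about three months away, the patients most likely to have none are those who die, decline or withdraw early. The rule removes them from the response rate, and nothing elsewhere in the protocol puts them back as non-responders. A patient with even one unscheduled scan stays in, so inclusion depends partly on whether someone happened to order imaging.

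What is at stake is how the 10-patient expansion will read. Anti-tumor effect is a secondary objective (section 1.2), and section 2.1 quotes response rates of 60-80% for FSRT alone, which is the natural comparison. A rate calculated only in patients who reached a scan can look better against that range than the same data over all treated patients. Early deaths still count as events in PFS (section 11.2) and appear in the death listings (section 7.3), but neither corrects the response percentage.

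**Working it through.** The plan states no response rate, power or missing-scan rate, so there is no figure to reproduce. The check has four steps.

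**1. When is the first scheduled scan?** Three months is taken as 91 days.

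| Anchor | Calculation | Day |
|---|---|---|
| Month-3 visit, from day 1 (5.7) | 1 + 91 | 92 |
| End of treatment = last FSRT fraction, day 5 | 5 + 91 | 96 |
| End of treatment = last TPI 287 dose, day 15 | 15 + 91 | 106 |

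Twelve weeks of life expectancy from day 1 is 1 + 84 = day 85. The scan falls 92 − 85 = 7, 96 − 85 = 11 or 106 − 85 = 21 days later. Calendar footnote g starts roughly 12-weekly follow-up after the final visit. Read as a first follow-up 12 weeks after that visit, it gives about day 15 + 30 + 84 = 129, which lengthens the wait.

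**2. Which way does exclusion act?** With x responders among n treated patients and m unscanned, the plan's rule gives x/(n − m) and the all-treated rate is x/n. An unscanned patient cannot meet a definition that needs two MRIs, so x is the same in both. Hence x/(n − m) ≥ x/n, with equality only if m = 0 or x = 0. A patient with one post-treatment scan but no confirmatory scan stays evaluable, so m counts only patients with no re-evaluation at all.

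**3. How large is the shift at n = 10?** The values of x and m are assumptions. Intervals are exact (Clopper-Pearson) 95%.

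| Responders | Unscanned | Reported under 11.1 | All treated | Shift (points) |
|---|---|---|---|---|
| 6 | 1 | 6/9 = 66.7% (29.9-92.5) | 6/10 = 60% (26.2-87.8) | 6.7 |
| 6 | 2 | 6/8 = 75.0% (34.9-96.8) | 60% | 15.0 |
| 6 | 3 | 6/7 = 85.7% (42.1-99.6) | 60% | 25.7 |
| 8 | 1 | 8/9 = 88.9% (51.8-99.7) | 8/10 = 80% (44.4-97.5) | 8.9 |
| 8 | 2 | 8/8 = 100% (63.1-100) | 80% | 20.0 |

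In the first block, two unscanned patients move the estimate from the bottom of the 60-80% range in section 2.1 to near its top, and three move it above.

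**4. How likely is at least one unscanned patient?** If each patient independently has probability q of no scan (assumed), the chance is 1 − (1 − q)^10. On average the rate is multiplied by about 1/(1 − q).

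| q | P(at least 1 of 10) | 1/(1 − q) |
|---|---|---|
| 5% | 40.1% | 1.05 |
| 10% | 65.1% | 1.11 |
| 20% | 89.3% | 1.25 |

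**The case against.** The strongest objection concerns what is being estimated. The treatment is aimed at brain lesions in patients with advanced systemic cancer. Someone who dies of extracranial disease before month 3 has an unknown intracranial response, and counting that person as a non-responder may understate the effect in the brain. With 6 responders and 2 unscanned, the rate in all 10, had everyone been scanned, could lie anywhere from 6/10 to 8/10. The plan's 75% is right if unscanned patients would have responded like the scanned ones. This stands in part: the exclusion is favourable relative to the all-treated rate, and not necessarily relative to the unknown intracranial rate. But the plan neither states nor defends that assumption, and it is hard to accept when the reasons for leaving (section 5.8) include progression and deterioration. Reporting both rates, with reasons for each missing scan, answers the point.

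Other objections limit the weight of the concern without removing it:

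- Response is not primary, objective response rate is not among the secondary endpoints in section 14.1, and no decision rule uses it. That is correct; the link is the anti-tumor objective and the purpose given for the expansion.
- Section 11.1 speaks of disease being re-evaluated, not scanned, and never uses the word denominator. The reading here is an inference, but a firm one, because the rule is exclusive and the categories need imaging. If clinical re-evaluation was meant, the text should say so.
- The life-expectancy criterion is an eligibility floor, not expected survival. The day counts show that a gap is possible, not how many patients fall into it.

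**Conclusion.** The concern holds. Followed as written, section 11.1 drops treated patients with no post-treatment assessment from the response rate, and no other section counts them as non-responders. Relative to all treated patients, the reported rate can only be higher or unchanged.

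The size depends on assumptions. One to three unscanned patients out of 10, with 6 responders, gives an increase of about 7 to 26 points. The upper figure needs 30% unscanned, and the confidence intervals overlap widely throughout. The direction does not depend on those assumptions. The consequence is moderate: it affects how a descriptive, non-primary result is read and does not affect dose finding or safety conclusions. The change should be made because it is cheap and the expansion is partly meant to show radiologic response.

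**What to change.** In sections 11.1 and 14.3:

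- Make all patients who received TPI 287 with FSRT the main response denominator, and count those with no post-treatment assessment as non-responders.
- Report the MTD cohort with an exact 95% interval, together with the number of patients who had no scan and the reason for each.
- Keep the re-evaluated patients as a sensitivity analysis.

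As a related clarification, section 5.8 says "Patients who are discontinued from the study will still be followed for disease progression", while section 5.7 and calendar footnote d run MRI only until a patient is off-study. The sponsor should state how these fit together.

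The denominator change is analysis wording only: no added patients, visits or scans. The off-study clarification is also wording; it would add scans only if the sponsor chose to continue MRI after a patient leaves. The price is a main response rate that may look less favourable and, if early deaths are mostly extracranial, may be conservative for effect in the brain. The sensitivity analysis and the listed reasons make that visible.

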5.4 Definition of Dose-Limiting Toxicity

Toxicities will be graded in severity according to the guidelines outlined in the NCI-CTCAE version 4.0. Dose limiting CNS and non-CNS (hematologic and non-hematologic) toxicities will be defined differently and will be based on events that occur during the study period. In order to be declared as dose-limiting toxicity, an adverse event must be related (definite, probable, or possible) to study treatment.

A dose-limiting toxicity (DLT) will be defined as any one of the following adverse events occurring within 8 weeks from last dose of radiation therapy:

CNS toxicities:

Acute CNS toxicities (occurring \leq 30 days after completing FSRT treatment):

• Any grade 3 or higher central nervous adverse events including but not limited to headache, dizziness, vertigo, new onset seizures, cerebral edema, cerebral hemorrhage, and new onset neurologic deficit.

Delayed onset CNS toxicities (occurring >30 days after completing FSRT treatment):

 Any grade 3 or 4 adverse event arising within the irradiated volume including but not limited to radiation necrosis or focal neurological deficits.

Non-CNS toxicities:

Non-hematologic toxicities:

- Any grade 3 or higher non-hematologic adverse event with the exception of alopecia, fatigue, and anorexia.
- Grade 3 or higher nausea and/or vomiting that persists ≥ 48 hours despite optimal medical management.

Hematologic toxicities:

- Grade 4 neutropenia lasting for \geq 7 days in duration
- Grade \geq 3 febrile neutropenia with/without infection

• Grade 4 thrombocytopenia

Dose escalation will be determined based on the occurrence of DLTs. For the purposes of determining whether to advance the dose levels, DLTs will be counted by patient. In the event of the development of any grade 3 or 4 toxicity felt to be at least possibly related to study drug, TPI 287 will be held until resolution to grade 1 or baseline assuming that occurs within 15 day window.

Dose escalation will follow the standard 3+3 design. The enrollment to next higher dose level will be delayed for 8 weeks after the completion of FSRT by the last patient enrolled at the dose level. This period of 8 weeks will allow monitoring potential delayed toxicities. Management and dose modifications associated with the above adverse events are outlined in Section 6. Dose escalation will proceed according to the following scheme. Dose-limiting toxicity (DLT) is defined above.

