5.9 Stopping Rules

The expected rate of neurologic death with FSRT alone is 13-14%. ^{24,25} The reported rate for symptomatic radiation necrosis is 7.7%. ²⁴ A higher rate of neurologic death (> 14%) or symptomatic brain necrosis (> 10%) in this study would imply that the combination of FSRT and TPI 287 is excessively toxic and not suitable for further clinical development. In addition grade \geq 3 delayed-onset toxicity in this study would imply that the combination of FSRT and TPI 287 is excessively toxic and not suitable for further clinical development. In addition, the results will be discussed with Cortice Bioscience, Protocol Monitoring Committee and IRB and study will be closed. In addition, occurrence of other delayed-onset treatment related grade 3 or higher CNS- toxicity will be monitored closely and reviewed with Protocol Monitoring Committee and IRB to determine whether discontinuation of trial is subsequently warranted.

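### Growth of an irradiated lesion counts as progression without a second scan and with no treatment-effect category, so radiation necrosis can be recorded as PD and as a PFS event

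*Combined protocol and SAP*

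**What the plan says.** Section 11.1 gives five response categories: CR, PR, MR, SD and PD. The three response categories need confirmation. For CR, "The tumor is no longer seen on two sequential MRI scans"; for PR, a 50% or larger "decrease in the product of two diameters of target lesions on two sequential MRIs"; MR has the same two-scan condition. PD is a "> 25% increase in the product of two diameters of target lesions", measured from the smallest product on study, or any new lesion. No second scan is asked for. The one proviso concerns steroids: "A concomitant decrease in steroid dose will rule out a progression designation at this point".

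Section 11 schedules a repeat scan for response only: "confirmatory MRIs will also be obtained 4 weeks following initial documentation of an objective response". It names an independent neuroradiologist and adds that "The evaluation of scans will be compared to and corrected with the patient's clinical course". Section 11.1 also plans a further reading by the RANO brain-metastasis criteria, once these are published.

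The protocol expects radiation necrosis elsewhere. Section 7.1.1 lists it as a possible late effect. Section 5.4 counts grade 3 or 4 delayed events in the irradiated volume as dose-limiting, "including but not limited to radiation necrosis or focal neurological deficits". Section 5.9 says that "symptomatic brain necrosis (> 10%) in this study would imply that the combination of FSRT and TPI 287 is excessively toxic", against a reported rate of 7.7%.

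Section 11.2 makes progression or death the PFS event. Section 14.1 lists the local control rate as a secondary endpoint. Neither local control nor local failure is defined.

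**The concern.** The plan treats growth of an irradiated lesion as an efficacy failure and names necrosis, which can produce that growth, as a toxicity. It has a written size rule for the first and none for deciding which of the two has occurred. Confirmation is also one-sided: shrinkage must be seen twice, growth once.

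Local control, PFS and response are at stake. These are the secondary measures by which a reader would judge whether TPI 287 adds to radiotherapy. If necrosis enters them as progression, they mix toxicity with tumour failure, and with about ten patients at the MTD one or two such cases are visible in the result. The distinction is hard to rebuild later. Section 5.7 schedules MRI only until the patient is off study, and section 5.8 removes patients whose progression needs therapy outside the protocol.

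**Working it through.** The plan states no figure for this point, and its analysis is descriptive (section 14.3), so there is no power or error rate to reproduce. The check reads the rules together and then sizes the effect.

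**1. How low the PD bar is.** If both diameters grow equally, a 25% rise in the product means growth per diameter of √1.25 − 1 = 0.118, about 12%. That is 20 mm × 0.118 = 2.4 mm for a 2 cm lesion and 50 mm × 0.118 = 5.9 mm for a 5 cm lesion, the largest eligible diameter (section 3.1).

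**2. An enlarging necrotic lesion followed through the rules.**

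| Rule | Effect |
|---|---|
| PD size rule (11.1) | Met on the first scan above 25% |
| Steroid proviso (11.1) | Blocks PD only if the dose was reduced; no effect if it was stable or increased |
| Clinical-course correction (11) | Could change the reading, but gives no criteria, no timing and no category to move it to |
| RANO reading (11.1) | Additional and conditional on publication; does not replace the PD rule |
| Confirmatory MRI (11) | Follows objective response only |
| PFS (11.2) | An uncorrected PD is an event |
| Local control (14.1) | Undefined; PD of an irradiated lesion is the likely reading, not a stated one |

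**3. Size in the expansion cohort.** Inputs: n = 10 (section 14.2) and a symptomatic necrosis rate of 7.7% (section 5.9).

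- One patient relabelled: 1/10 = 10 percentage points of local control, if the rate is per patient and local failure is taken as PD. With up to three lesions per patient (section 3.1) a per-lesion rate has 10 to 30 lesions, so one lesion moves it by 1/30 to 1/10, or 3.3 to 10 points. The plan does not say which denominator applies.
- Expected necrosis cases: 10 × 0.077 = 0.77.
- P(at least one case) = 1 − (1 − 0.077)^10 = 0.55.
- Over an assumed range of 5% to 20%: 1 − 0.95^10 = 0.40, to 1 − 0.80^10 = 0.89.

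These are chances that a necrosis case occurs, not that it is mislabelled. They become chances of mislabelling only if each case exceeds 25% growth, steroids were not reduced and the clinical correction does not intervene. In the other direction, 7.7% covers symptomatic necrosis only, and asymptomatic necrosis that enlarges a lesion would add cases.

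**The case against.** The strongest reply is that PD is not a bare one-scan rule. The steroid proviso, the independent neuroradiologist, the clinical-course correction and the planned RANO reading all stand in the text. When necrosis is symptomatic, the clinical course gives the reader something to work with. This stands in part: these provisions soften the gap, but none says when an enlarging irradiated lesion is treatment effect.

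A second reply is that response is not the primary endpoint and that dose finding is largely insulated. The DLT window closes 8 weeks after radiotherapy, while scheduled follow-up MRIs come every three months after treatment ends, so a PD call at a scheduled scan cannot hide an in-window DLT. That stands, and it limits the point to the secondary endpoints.

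A reader might go further and infer that a PD label lowers the necrosis count in section 5.9, or that toxicity rising with dose would pass for poor efficacy. The documents do not support this. Response and toxicity are separate records, and a lesion can be PD and also a necrosis adverse event. Adverse events are assessed at follow-up visits (section 10), late in-field CNS toxicity is to be recorded (section 5.4), and treatment-related toxicities present at withdrawal are followed (section 5.8). Section 5.9 also counts symptomatic necrosis only, so asymptomatic growth never enters it. What remains is that the plan does not say how the two records relate.

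**Conclusion.** The concern holds for response, PFS and local control. As written, necrosis that enlarges an irradiated lesion by more than 25% while steroids are stable or increased meets PD and is a PFS event, unless a correction without criteria intervenes.

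To say that necrosis *is* recorded as local failure would go too far, because local failure is undefined; that it probably would be is a fair reading.

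The size is 10 points of per-patient local control for each case among 10 patients, with a 0.55 chance of at least one necrosis case at the cited 7.7%. Both figures rest on the conditions set out in the working. The point concerns secondary endpoints in a descriptive phase 1 analysis, so it is an inexpensive improvement, not a flaw that undermines the trial.

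**What to change.** Add one paragraph to section 11.1, for the response, local-control and PFS analysis only:

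- Record growth above 25% confined to a study-irradiated lesion as *in-field enlargement*. Classify it as progression, treatment effect or indeterminate from the next scheduled MRI, the clinical course and the reading of the neuroradiologist already named.
- If progression is confirmed, date PD to the first scan. If there is no later scan, classify as indeterminate.
- Define local failure per irradiated lesion, and state whether the rate is over patients or lesions. Count indeterminate cases as failures in the main local-control and PFS analysis, and show a sensitivity analysis without them.
- State that a PD label does not replace adverse event recording. Symptomatic necrosis is recorded as an adverse event when diagnosed, whatever the response label, and only such events enter the section 5.9 rate. Report indeterminate or asymptomatic enlargement separately.

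The last limit matters. In 36 patients, the escalation maximum, a rate above 10% means at least 4 events (3/36 = 8.3%, 4/36 = 11.1%). At a true 7.7% the exact binomial P(at least 4) is 0.30. If indeterminate cases in an assumed further 5% or 10% of patients were counted, the rate would be 12.7% or 17.7% and the probability 0.69 or 0.90, in a rule that closes the study.

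The cost is the paragraph, one case report form field and one sensitivity analysis, with no extra scan or reader. The downside is that some patients' final response label is known one scan later.
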